#### **4.2 Scientific Rationale for Study Design**

The current treatment of osteoarthritis relies on joint stability and non-operative control of inflammation. Oral non-steroidal anti-inflammatory (NSAID) options remain the initial line of treatment. When oral NSAIDs have failed, treatments with intra-articular

injectable corticosteroids for local pain management have proven successful for a short period of time, though evidence exists that their long-term use can be detrimental.

Other non-surgical treatment options include the injection of hyaluronic acid or other gels and biologics such as platelet rich plasma. While these treatments do provide pain relief, their precise mechanism of action is not known.

Joint arthroplasty is a definitive and successful surgical intervention typically offered to age appropriate patients after other less invasive measures have failed. However, this is substantial surgical intervention and possesses the inherent risks of any such procedure. Concern also exists regarding the longevity of knee arthroplasty, particularly in the younger, more active population.

Cell therapies have been increasingly employed to treat osteoarthritis, which include various forms of autologous (harvested from the same patient's body) mesenchymal stem cell injections. However, while this procedure has shown better outcomes than other non-surgical treatments, questionable reproducibility and the limited supply of stem cells limits the potential improvements to this valuable technique.

A large case series (41 subjects, 75 knees) with different biologics injections, most of which were autologous bone marrow concentrate (BMAC) + adipose derived stromal vascular fraction (SVF) were injected into the knee joint. Visual analog score (VAS), knee injury and osteoarthritis score (KOOS), international knee documentation committee (IKDC) and Lysholm knee Scores (patient reported outcome measures, PRO's) were all improved in the treated group [1]. ***Better outcomes were noted in those with lower degrees of osteoarthritis.***

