#### **5.1.1 Inclusion Criteria**

1. Age  $\geq 40$  but  $\leq 70$  years old
2. Males and Females

3. Recent knee radiograph of the targeted knee (standing AP lateral and sunrise view)
4. Diagnosis of OA in the targeted knee (radiographic evidence of OA in the medial and/or lateral tibiofemoral compartment, which would include one or more osteophytes on a standard radiograph taken within 3 months). Subjects may have concomitant patellofemoral but they must have grade II or higher medial or lateral tibiofemoral knee OA and the primary pain must be related to the tibiofemoral arthritis.
5. Continued OA pain in the targeted knee despite conservative measures (per treating provider's discretion)
6. Average daily VAS  $\geq 3$
7. Kellgren-Lawrence system of Grade II, III, or IV
8. Females of childbearing potential (FCBP) only, must have a negative pregnancy test done at screening prior to enrollment. FCBP is defined as any premenopausal female unless they have had a surgical sterilization procedure including, but not limited to, hysterectomy, tubal ligation or oophorectomy.
9. Women and men of child-producing potential must agree to use acceptable contraception methods for the duration of the trial such as birth control pills or condoms with spermicide.

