### **6.2.1 Randomization Methods**

Treatment assignments will be generated using a pseudo-random-number generator with randomly permuted blocks. This method serves to balance the treatment group assignments over the course of the study to ensure that the desired number of subjects will be allocated to each of the treatment groups at any time point during the randomization period. The statistical method for implementation of the randomization plan will be detailed in the Statistical Analysis Plan (SAP). Briefly, after obtaining informed consent, all eligibility confirmation data will be entered into the RAVE EDC database by the delegated study staff. If the subject meets all eligibility criteria, computer randomization will be performed and the coordinator will be provided with an audit trail of the process including a verifiable link between the unique study ID and treatment assignment. The application will be password protected with access restricted to designated MILES personnel.

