### **6.2.2 Implementation of Randomization and Blinding**

Subjects randomized to Arm 1 or Arm 2 will undergo a procedure (bone marrow aspiration or liposuction) but will only receive one of the possible injections. For instance, subjects randomized to the control portion of Arm 1 will undergo a bone marrow aspiration but will receive a blinded corticosteroid injection. The bone marrow aspirate will still be processed and used to help quantify cell characteristics. Subjects randomized to Arm 3 will not undergo the procedures mentioned above. They will be blinded and receive either the stem cell injection or the corticosteroid injection.

Four hundred eighty subjects will be randomly assigned to treatment in this multicenter trial. Subjects at each clinical site will be randomized to ensure the trial is single-blind with a 1:1 allocation ratio across the four treatment groups.

One hundred twenty subjects will be randomized at each of 4 clinical sites. Arm 1: Forty subjects will be randomized with a 3:1 allocation ratio (bone marrow derived MSCs versus corticosteroid injection; 30:10). This same implementation plan will be used to randomize 40 subjects to Arm 2 (adipose derived MSCs versus corticosteroid injection) with a 3:1 allocation ratio and to randomize 40 subjects to Arm 3 (umbilical cord tissue MSCs versus corticosteroid injection) with a 3:1 allocation ratio.

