#### **9.2 Sample Size Determination**

The total estimated sample size for the proposed intention-to treat, parallel-group, multicenter, randomized, controlled trial is 480 subjects. The primary endpoints are Visual Analog Scale (VAS) pain score and the pain subsection of the Knee Injury and Osteoarthritis Outcomes (KOOS). The sample size calculations are based on improvements (from baseline to 1-year) in the visual analog scale (VAS) pain score and total KOOS. Total KOOS was used as a proxy and should ensure that the study is amply powered.

Assuming a decline of 1 point on average in pain in the Control arm (corticosteroids) and a decline on average of 2.5 points in a treatment arm (mesenchymal stem cells) and an estimated standard deviation on change of 3.5, the proposed sample sizes (n=121 subjects

per group or 484 total subjects) will provide 91% power to detect a difference on change of 1.5 points at the two-sided 5% significance level if the true difference between treatment groups is 1.5 points (two-sided two-sample equal variance t-test).

Assuming an increase of 10 points on average in total KOOS in the Control arm (corticosteroids) and an increase on average of 20 points in a treatment arm (mesenchymal stem cells) and an estimated standard deviation on change of 20, the proposed sample sizes (n=121 subjects per group or 484 total subjects) will provide 97% power to detect a difference on change of 10 points at the two-sided 5% significance level if the true difference between treatment groups is 10 points (two-sided two-sample equal variance t-test).

Each of the four participating sites will accrue 30 subjects to each of the 4 treatment groups. Cohort retention is expected to be 90% at 1-year.

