#### **9.3.2 Primary and Secondary Efficacy Analyses**

Eight separate repeated-measures analysis will be performed on the eight efficacy variables described above. Each of the eight variables will be used as a dependent variable. The following model building method will be used for each analysis. Using Statistical Analysis System (SAS) MIXED Procedure (version 9.4; SAS Institute, Cary, NC), a linear mixed model will be fit on each efficacy variable. The model will include site, treatment arm, time on study (baseline and 1, 3, 6, 9

and 12 months on study), and treatment arm by time interaction as fixed effects. Subject ID will be the random effect. A compound-symmetric variance-covariance form in repeated measurements will be assumed and robust estimates of the standard errors of parameters will be used to perform statistical tests and construct 95% confidence intervals. The model-based means are unbiased with unbalanced and missing data, assuming missing data are non-informative. A P-value  $\leq 0.05$  will be considered statistically significant for all the terms in the mixed model. The statistical test for interaction between time on study and treatment will be the overall hypothesis test to determine whether efficacy variables in the four treatment arms changed significantly during 12 months of follow-up. If mean scores in the treatment arms are consistently different or similar over time (i.e., no statistical interaction) then the main effect test for treatment will be used as the primary hypothesis test to compare the treatment arms. The primary study results from this model will be the mean score and 95% confidence interval for each of the 4 treatment arms and the treatment mean differences and 95% confidence intervals.

Assuming a significant treatment effect on efficacy score change is identified (i.e., the interaction test is significant at  $P = 0.05$ ) then the six pairwise treatment comparisons on pain score change will be performed. A Bonferroni correction ( $p=0.05/6=0.0083$ ) for multiple comparisons will be applied. Specific statistical tests on efficacy score change will be done within the framework of the mixed effects linear model. All statistical tests will be 2-sided and adjusted for multiple comparisons. The same Bonferroni method will be used if the statistical interaction between treatment group and time on study is not significant but the main effect test for treatment is significant.

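### The efficacy model omits Kellgren-Lawrence grade; adjusting for grade and grade-by-time could recover a modest amount of precision, to the extent that grade predicts change in pain

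*Combined protocol and SAP*

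**What the plan says.** Section 9.3.2 defines one linear mixed model for each of eight efficacy variables. Of the fixed effects it says "The model will include site, treatment arm, time on study", and it adds the arm-by-time interaction. Subject is the random effect, the covariance is compound-symmetric and standard errors are robust. Baseline is the first of the six repeated time points, so it is part of the outcome and not a covariate.

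On testing, the section states: "The statistical test for interaction between time on study and treatment will be the overall hypothesis test". If there is no interaction, the treatment main effect becomes the primary test. Six pairwise comparisons follow at 0.05/6 = 0.0083. Section 9.3.3 takes age, sex and ethnicity as subgroup factors.

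Grade appears in two other places. Inclusion criterion 7 in Section 5.1.1 reads "Kellgren-Lawrence system of Grade II, III, or IV". Section 4.2, describing a case series of 41 subjects (75 knees) given mixed biologic injections, stresses: "Better outcomes were noted in those with lower degrees of osteoarthritis".

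On allocation, Section 6.2.1 says "Treatment assignments will be generated using a pseudo-random-number generator with randomly permuted blocks", and Section 6.2.2 describes randomization at each site "with a 1:1 allocation ratio across the four treatment groups". Neither section names grade as a stratum.

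**The concern.** The protocol restricts entry by radiographic grade and draws attention to a report that severity relates to outcome. As described, neither the randomization nor the analysis then uses grade. If grade does predict how much pain changes over the year, two things follow. Variation that could be explained stays in the residual of the change contrasts. Any chance difference in grade mix between groups also adds to the random error of the estimated treatment differences.

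Precision matters most at the pairwise step. The stated 91% VAS power is for a single comparison at alpha 0.05, whereas the pairwise comparisons are to be judged at 0.0083, where the margin is much thinner.

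**Working it through.** **Inputs.** Section 9.2 gives, for VAS, "an estimated standard deviation on change of 3.5" and power "if the true difference between treatment groups is 1.5 points". For total KOOS, the proxy for KOOS pain, it gives SD 20 and difference 10. Both use n = 121 per group, two-sided 5%, and an equal-variance two-sample t-test. The operational number is 120 per group (30 at each of 4 sites), and expected retention is 90%, so 0.9 × 120 = 108. The share of the variance of change explained by grade, R², is not in the documents; it is assumed to be 0, 2%, 5% or 10%.

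**Step 1: reproduce the plan.** The noncentral t calculation at n = 121 and alpha 0.05 gives 91.3% for VAS and 97.2% for total KOOS. The stated 91% and 97% are confirmed.

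**Step 2: which effect of grade matters.** Write the grade effect at visit t as g(t). In the change from baseline to month 12 it contributes g(12) − g(0).
- If g is constant over time, this is zero: a stable effect on pain level cancels.
- If g varies over time, the difference remains in the change score, and only a grade-by-time term removes it.

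A simulation of the planned model (4 × 120 subjects, six times, compound symmetry, robust standard errors, 100 runs per setting) gave these mean standard errors for the VAS difference in change:

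| Setting | No grade | Grade main effect only | Grade + grade × time |
|---|---|---|---|
| R² = 10%, complete data | 0.449 | 0.449 | 0.427 |
| R² = 10%, 10% dropout | 0.463 | 0.461 | 0.439 |
| R² = 0, 10% dropout | 0.463 | 0.463 | 0.463 |

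With complete data, the estimates without grade and with a grade main effect agreed to rounding error.

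**Step 3: size of the gain with grade-by-time in the model.** Residual SD = 3.5 × √(1 − R²). SE = residual SD × √(2/120). Equivalent n = 120/(1 − R²). Power is from the two-sample t-test for VAS, difference 1.5.

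| R² of change (assumed) | SE | Equivalent n per group | Power, n = 120, alpha 0.05 | Power, n = 120, alpha 0.0083 | Power, n = 108, alpha 0.0083 |
|---|---|---|---|---|---|
| 0 | 0.452 | 120 | 91.1% | 74.5% | 68.6% |
| 2% | 0.447 | 122 | 91.6% | 75.5% | 69.8% |
| 5% | 0.440 | 126 | 92.4% | 77.1% | 71.5% |
| 10% | 0.429 | 133 | 93.6% | 79.8% | 74.4% |

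For total KOOS at n = 120 and alpha 0.0083, power goes from 88.6% to 89.4%, 90.4% and 92.1%.

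**Step 4: chance imbalance on the outcome scale.** If 33% to 40% of subjects share one grade (assumed), the 95% range for the difference in that share between two groups of 120 is ±1.96 × √(2p(1 − p)/120), about ±12 percentage points. Its contribution to the VAS difference in change has SD √R² × 3.5 × √(2/120): 0.06, 0.10 and 0.14 points for R² of 2%, 5% and 10%. The design difference is 1.5 points and the unadjusted SE is 0.452.

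**The case against.** The evidence that grade predicts change is thin. Section 4.2 reports one small series, refers to degrees of osteoarthritis without naming Kellgren-Lawrence, and describes no randomized comparison. This stands: the benefit is a possibility and its size is unknown.

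A reader might infer that grade is an effect modifier that the protocol itself identifies. The text does not support that. A series without a control comparison cannot separate better prognosis from a larger treatment effect. Section 2.2 also raises donor age as a possible influence on adipose cell analyses, and age is already a subgroup factor.

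A reader might also infer that any imbalance in grade passes directly into the treatment differences. Step 2 shows that for change contrasts only the relation of grade to change can do so. Step 4 shows that the contribution is small against 1.5 points, and under randomization it is already reflected in the standard error.

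Two further objections stand in part. The criterion guarantees that each knee is graded, and Section 6.2.1 has eligibility confirmation data entered in the EDC, but no text says that the individual grade is held as an analysis variable. Section 9.3 calls itself a summary of an SAP, and Section 6.2.1 defers randomization detail to it; no separate, fuller SAP is in the supplied text, so grade could appear there. Sections 9.3.2 and 9.3.3 do, however, list model terms explicitly and leave it out.

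On the other side, a grade main effect is not useless. The fallback treatment main-effect test and the mean scores by arm concern levels, where a stable grade effect does not cancel.

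**Conclusion.** The point holds as a modest efficiency and chance-imbalance improvement. Randomization keeps the planned test valid without grade; the omission is neither a bias nor an error.

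If grade explains 2% to 10% of the variance of change, VAS power rises by 0.5 to 2.5 percentage points at alpha 0.05 and by about 1 to 5 points at 0.0083, with 120 per group. If grade does not predict change, the gain on the change contrasts is nil. These figures rest on the assumed R² and on the plan's own t-test approximation, SD and difference. The possible gain for the fallback main-effect test was not quantified, because the documents give no variance for pain level.

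The documents do not support calling grade an established prognostic factor, and they do not make a grade subgroup analysis necessary.

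**What to change.** Before unblinding, prespecify Kellgren-Lawrence grade as a three-level categorical fixed effect (II, III, IV), together with its interaction with time, in the primary and secondary models of Section 9.3.2; or state why grade is left out. The interaction is the essential part, because a main effect alone leaves the treatment-by-time contrast essentially unchanged. If the full SAP already contains these terms, bring Section 9.3.2 into line with it. A grade subgroup analysis in Section 9.3.3 is optional.

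The cost is SAP wording, a check that the individual grade is captured in the EDC, and 12 extra parameters in each of the eight models: 3 − 1 = 2 for grade and 2 × 5 = 10 for grade-by-time, with 480 subjects.

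### Site is modelled only on score level, so it does no work in the tests on change; adding site-by-time is a nearly free, minor gain in efficiency

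*Combined protocol and SAP*

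**What the plan says.** **Allocation.** Section 6.2.2: "Subjects at each clinical site will be randomized to ensure the trial is single-blind with a 1:1 allocation ratio across the four treatment groups". It then sets 120 subjects per site, 40 in each procedure arm, split 3:1 between cell product and corticosteroid. Section 9.2 gives the same count: "Each of the four participating sites will accrue 30 subjects to each of the 4 treatment groups".

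**Model.** Section 9.3.2 fits a linear mixed model to each of eight efficacy variables. Its fixed effects are site, treatment arm, time "and treatment arm by time interaction as fixed effects". Subject is random, the covariance is compound-symmetric and the standard errors are robust. Time has six levels, baseline included (section 9.3.3 gives the coding). No other interaction appears in the main model.

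**Tests.** The overall test is treatment-by-time. If it is significant, six pairwise comparisons of change follow at 0.05/6 = 0.0083. If it is not, the treatment main effect becomes the primary test, and the same pairwise correction applies when that effect is significant.

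**Sample size.** Section 9.2 uses a "two-sided two-sample equal variance t-test" on change, with no site term.

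**The concern.** When allocation is balanced within site, differences between sites cannot contribute to the sampling error of a treatment difference. The analysis benefits from this only if the model removes those differences from the residual for the quantity being tested. Here that quantity is change from baseline, while the site term acts on level. Any site difference in mean change therefore stays in the residual. Robust standard errors do not remove it, because they are built from the same subject residuals.

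Such differences are plausible. Section 5.1.1 admits Kellgren-Lawrence grades II to IV and leaves part of the entry judgement to the treating provider. Section 4.2 cites a case series with better outcomes in milder disease. Case mix could therefore differ by site, although the documents put no number on it.

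At stake is some precision in the tests on change. The treatment-by-time test also decides whether the analysis moves to the fallback.

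**Working it through.** **1. The plan's own figures.** Section 9.2 gives, for VAS, difference 1.5 and "an estimated standard deviation on change of 3.5"; for total KOOS, difference 10 and "an estimated standard deviation on change of 20"; n = 121 per group, two-sided 5%.

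- VAS: SE = 3.5 × √(2/121) = 0.450, and 1.5/0.450 = 3.33. Noncentral t power is 91.3%. The plan: "will provide 91% power to detect a difference on change of 1.5 points at the two-sided 5% significance level".
- KOOS: SE = 20 × √(2/121) = 2.571, and 10/2.571 = 3.89. Power is 97.2%. The plan: "will provide 97% power to detect a difference on change of 10 points at the two-sided 5% significance level".

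Both reproduce.

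**2. Why site drops out.** Under 9.3.2 the mean for site s, arm a, visit t is μ + γ(s) + α(a) + τ(t) + ατ(a,t). Subtracting the baseline mean leaves τ(t) − τ(0) + ατ(a,t) − ατ(a,0). The site term γ(s) has gone.

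**3. Effect on the standard error.** Let R² be the share of the variance of 12-month change that lies between sites. It is an assumption, because the documents do not give it. With 30 per group in every site, each arm's mean change contains the same average of site effects, so these cancel from the treatment difference.

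- True variance of the difference: 2σ²(1 − R²)/120.
- Variance reported by the planned model: about 2σ²/120.
- Planned SE relative to the SE with site-by-time: 1/√(1 − R²).

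**4. Effect on power.** Use the noncentral t with SD × √(1 − R²), total SD held at 3.5 (VAS) or 20 (total KOOS), and alpha 0.0083. The columns for 108 per group apply the 90% retention in section 9.2 (0.9 × 120).

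| Assumed R² | Site SD of VAS change, 3.5√R² | SE ratio | VAS power, n = 120 | VAS power, n = 108 | KOOS power, n = 120 |
|---|---|---|---|---|---|
| 0 | 0 | 1.000 | 74.4% | 68.6% | 88.6% |
| 1% | 0.35 | 1.005 | 75.0% | 69.2% | 89.0% |
| 2% | 0.49 | 1.010 | 75.5% | 69.7% | 89.4% |
| 5% | 0.78 | 1.026 | 77.1% | 71.5% | 90.4% |
| 10% | 1.11 | 1.054 | 79.8% | 74.4% | 92.1% |
| 20% | 1.57 | 1.118 | 85.2% | 80.3% | 95.2% |

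The first row is the power of the planned model at every R². The drop from 91% to 74.4% comes almost entirely from the 0.0083 level and is not caused by the site term.

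**5. Simulation check.** The set-up was 4 sites × 4 groups × 30 subjects, six visits, compound-symmetric weights, subject-level sandwich SE, no treatment effect, complete data and 700 trials per setting. The 12-month estimate had the same empirical SD under both models.

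| R² | Empirical SD | Mean SE, site main effect (ratio to empirical SD) | Mean SE, site-by-time (ratio to empirical SD) |
|---|---|---|---|
| 0 | 0.447 | 0.450 (1.01) | 0.449 (1.01) |
| 2% | 0.448 | 0.448 (1.00) | 0.442 (0.99) |
| 5% | 0.432 | 0.449 (1.04) | 0.436 (1.01) |
| 10% | 0.429 | 0.450 (1.05) | 0.426 (0.99) |
| 20% | 0.398 | 0.450 (1.13) | 0.400 (1.01) |

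The Monte Carlo error of an empirical SD is about 1/√1400 = 2.7%. The runs therefore confirm the direction at larger shares but cannot resolve shares of 5% or less; there the formula is the better guide. At R² = 20% the planned 12-month contrast rejected 2.3% of null trials at nominal 5%, against 4.7% with site-by-time. With 10% dropout (400 trials, R² = 10%) the estimates were almost the same under both models, and the planned SE was 0.465 against 0.441, about 5.5% larger.

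The overall 15-df test used an uncorrected sandwich. In the complete-data runs it rejected 5.0 to 7.3% of null trials under the planned model and 5.6 to 8.9% with site-by-time (Monte Carlo error √(0.05 × 0.95/700) = 0.8 points). Some of these rates exceed 5% under either model, including at R² = 0 to 2%, where the site term hardly matters. I read this as a feature of the uncorrected robust test rather than of the missing term.

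**The case against.** **The loss may be zero.** A reader might infer that the standard errors for change are simply too wide. The documents do not support that. If sites do not differ in mean change, the planned SE is correct (0.450 against an empirical 0.447). This objection stands, so the point must be conditional.

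**Large shares are extreme.** A reader might take the 20% row as a fifth of the subjects thrown away. That row needs a between-site SD of 1.57 VAS points, more than the 1.5-point treatment difference the trial is sized on. Nothing in the documents supports it. It marks the end of the range and is not an expectation.

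**The plan may lose nothing against its own target.** Section 9.2 does not say whether 3.5 is a total or a within-site SD. If it is total, the planned model delivers the assumed SE and site-by-time only adds precision. If it is within-site, the planned SE is larger than assumed; at a 10% share it would be 3.5 × √(2/120) × 1.054 = 0.476 instead of 0.452. The ambiguity stands, and the power column takes the first reading.

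**Site is not ignored everywhere.** A reader might infer that the stratification goes unused. The fallback treatment main-effect test compares levels and is adjusted for site, as are the arm means. This also stands.

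**The text is a summary.** Section 9.3 describes itself as a summary of a fuller SAP. If that SAP already has the term, the point is closed.

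None of this gives a reason to leave the term out.

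**Conclusion.** The point holds as a minor matter of efficiency. With complete data, site as specified does no work in the treatment-by-time test or the pairwise tests on change, although the trial balances allocation by site. If sites differ in mean change, the standard errors for change are conservative. The treatment estimate is unbiased, and the omission does not inflate type I error.

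The size depends on an input the documents do not give. For shares of 1 to 5% the planned SE is 0.5 to 2.6% too large, and VAS power at 0.0083 with 120 per group is 0.6 to 2.7 points lower than it could be. At 10% the figures are 5.4% and 5.4 points, and at 0 there is no loss. They assume 30 per group in every site, complete data and a total SD of 3.5. The power figures are for a single pairwise comparison and leave out the preceding overall test.

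**What to change.** Add site-by-time to the fixed effects in section 9.3.2, and in the full SAP if it is absent there, for all eight efficacy variables. Make the change before the data are analysed.

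The cost is (4 − 1) × (6 − 1) = 15 parameters against up to 480 × 6 = 2,880 observations, so the loss of degrees of freedom is negligible. No data collection or subject is affected. In balanced, complete data the treatment estimates for change stay the same and only their standard errors move.

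When making the edit, state whether the SD of 3.5 in section 9.2 is total or within-site, and name the small-sample correction, if any, for the robust covariance in the 15-df overall test.

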## List of Abbreviations

ADP	Adipose Tissue
ADSC	Adipose Derived Stem Cells
AE/SAE/UP	Adverse Event/Serious Adverse Event/Unanticipated Problem
BMAC	Autologous Bone Marrow Concentrate
BMI	Body Mass Index
CDC	Centers for Disease Control
CFR	Code of Federal Regulations
CRF/eCRF	Case Report Form/electronic Case Report Form
CRO	Contract Research Organization
CSI	Corticosteroid Injections
DHHS	Department of Health and Human Services
DOD	Department of Defense
DSMB	Data Safety Monitoring Board
FDA	Food and Drug Administration
FCBP	Female of Child Bearing Potential
GCP	Good Clinical Practices
GEE	Generalized Estimating Equations
GMP	Good Manufacturing Practices
HIPAA	Health Insurance Portability and Accountability Act
ICF	Informed Consent Form
ICH	International Conference on Harmonization
IKDC	International Knee Documentation Committee
IND	Investigational New Drug
IRB	Institutional Review Board
KOOS	Knee Injury and Osteoarthritis Outcome Score
MAR	Missing at Random
MC3M	Marcus Center for Therapeutic Cell Characterization and Manufacturing
MedDRA	Medical Dictionary of Regulatory Activities
MRI	Magnetic Resonance Imaging
MSCs	Mesenchymal Stem Cells
NCI-CTCAE	National Cancer Institute-Common Terminology Criteria for Adverse Events
NIH	National Institutes of Health
NSAIDs	Non-Steroidal Anti-Inflammatory

OA	Osteoarthritis
OHRP	Office for Human Research Protections
PHI	Personal Health Information
PI	Principal Investigator
PRO	Patient Reported Outcomes
PRP	Platelet Rich Plasma
PSIS	Posterior Superior Iliac Spine
RCT	Randomized Controlled Trial
RPM	Revolutions per Minute
SAP	Statistical Analysis Plan
SAS	Statistical Analysis System
SoA	Schedule of Activities
SVF	Stromal Vascular Fraction
UCT	Umbilical Cord Tissue
UP	Unanticipated Problem
USA	United States of America
VA	Veteran's Administration
VAS	Visual Analog Scale

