Missing values will be excluded from the repeated measures analyses. Unknown values for ethnicity and gender will be included as a separate unknown category in the models if they represent more than 5% of the subjects.

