### **9.3.3 Efficacy Analyses across Subgroups**

The heterogeneity of treatment effects across age, sex, and ethnicity will be evaluated using a statistical test for interaction terms. Specifically, effects of treatment in subgroups will be determined by including the additional interaction terms between treatment and the three subgroups (age, sex, and ethnicity) in the repeated measures model described above for the eight efficacy variables.

The following variables will be treated as categorical variables in all of the linear mixed models.

- Treatment arms: CSI (reference), BMAC, ADP, UCT
- Age:  $\leq 65$  (reference) vs.  $>65$
- Sex: female vs male (reference)

- Ethnicity: Hispanic vs non-Hispanic
- Time: 0, 1, 2, 3, 4, 5 representing baseline and 1, 3, 6, 9 and 12 months follow-up visits

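### Section 9.3.2 calls the model means unbiased under non-informative missingness, but under missing at random this also needs the assumed compound-symmetric covariance to be right

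*Combined protocol and SAP*

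**What the plan says.** Section 9.3.2 plans the same linear mixed model for each of the eight efficacy variables, including both primary ones (VAS pain and KOOS pain). Fixed effects are site, arm, time and arm by time. Time is categorical (section 9.3.3): "Time: 0, 1, 2, 3, 4, 5 representing baseline and 1, 3, 6, 9 and 12 months follow-up visits". Baseline is therefore one of the six modelled responses.

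The within-subject correlation is described twice. First, "Subject ID will be the random effect". Second, "A compound-symmetric variance-covariance form in repeated measurements will be assumed and robust estimates of the standard errors of parameters will be used".

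On missing data the section says: "The model-based means are unbiased with unbalanced and missing data, assuming missing data are non-informative". It adds: "Missing values will be excluded from the repeated measures analyses". It does not say whether non-informative means missing completely at random or missing at random. The List of Abbreviations includes MAR ("Missing at Random"), but section 9 does not use the term.

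The inference rests on this model: "The statistical test for interaction between time on study and treatment will be the overall hypothesis test". The six pairwise comparisons are made within the same model. Section 9 names no alternative covariance and no fallback. Section 9.2 expects 90% retention at 1 year.

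**The concern.** Under missing at random, a likelihood-based mixed model in effect predicts each subject's missing scores from the scores already observed. The assumed covariance sets the weights in that prediction. If the covariance is wrong, the weights are wrong, and the estimated means shift when dropout depends on earlier scores. A robust (sandwich) variance estimates the sampling variability of those shifted means and does not move them back. The section's sentence on unbiasedness leaves this condition out.

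Compound symmetry is a strong assumption for this design:

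- It gives a 1-month gap and a 12-month gap the same correlation.
- It gives every visit the same variance. Section 5.1.1 requires an average daily VAS of at least 3 at entry, and baseline outcomes are collected at screening. This tends to narrow the baseline spread of VAS but not the later spread.
- Together these make the SD of change the same at every follow-up visit. The planning value in section 9.2 ("an estimated standard deviation on change of 3.5") would have to hold at month 1 as well as at month 12.

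At stake is a modest, avoidable bias in the 12-month treatment differences if loss differs between arms.

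**Working it through.** **1. The plan's own figures.** Inputs from section 9.2: VAS difference 1.5, SD of change 3.5, n = 121 per group, two-sided 5%.

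- VAS: SE = 3.5 × √(2/121) = 0.450; 1.5/0.450 = 3.33; power ≈ Φ(3.33 − 1.96) = 91.5%, or 91.3% by noncentral t. Stated: 91%.
- Total KOOS: SE = 20 × √(2/121) = 2.57; 10/2.57 = 3.89; power ≈ Φ(3.89 − 1.96) = 97.3%, or 97.2% by noncentral t. Stated: 97%.

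Both reproduce. They come from a two-sample t-test, so the covariance form does not enter.

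**2. Is the double description harmful?** With a random-intercept variance a, a compound-symmetric covariance c and a residual variance e, the marginal covariance is V = (a + c)J + eI. Only a + c enters. The triples (a, c, e) = (4, 0, 5), (2, 2, 5) and (0, 4, 5) all give variance 9 and covariance 4. V is the same, so means, differences, tests and intervals are the same.

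**3. Why the covariance matters under missing at random.** Assume SD 3 at each visit (not in the documents). Then 3.5² = 2 × 9 × (1 − ρ), so the baseline-to-month-12 correlation is ρ = 1 − 12.25/18 = 0.319. Suppose correlation decays exponentially in months, r(m) = 0.319^(m/12). The 15 pairwise correlations among months 0, 1, 3, 6, 9 and 12 sum to about 9.05, so a compound-symmetric fit to complete data uses their average, about 0.60. Take a subject last seen at month 9 (five scores observed):

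- Compound symmetry weights each of the five deviations by 0.603/(1 + 4 × 0.603) = 0.18.
- The true structure weights the month-9 deviation by 0.319^(3/12) = 0.75 and the others by 0.

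If that subject is 2 points above the arm mean at month 9 and on the mean before, the implied month-12 deviations are 0.35 and 1.50.

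**4. Size in large samples.** The simulation used 200,000 subjects per arm, two arms, and saturated arm-by-time means without a site term. The true 12-month difference was −1.5. Dropout was monotone, with logistic slope 0.6 per VAS point on the last observed score. SD, correlation shape, dropout slope and mechanism are assumptions. The table shows the bias in the 12-month change difference when compound symmetry is fitted; negative means the benefit is exaggerated.

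| True correlation | Dropout mechanism | 10% loss per arm | 30% loss per arm |
|---|---|---|---|
| Any | Completely at random | ≤0.01 in size | ≤0.01 in size |
| Compound symmetry | Any of those below | ≤0.01 in size | ≤0.01 in size |
| AR(1) by visit | Same in both arms | +0.02 | +0.04 |
| AR(1) by visit | Score-dependent in control only | −0.06 | −0.15 |
| AR(1) by visit | Opposite directions by arm | −0.09 | −0.24 |
| Exponential in months | Same in both arms | +0.01 | +0.02 |
| Exponential in months | Score-dependent in control only | −0.07 | −0.22 |
| Exponential in months | Opposite directions by arm | −0.14 | −0.40 |

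With the correct covariance, the estimate stayed within about 0.015 of the complete-data value throughout.

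The sign can reverse. With subject-specific slopes and loss of 15% v 5% or 20% v 10%, compound symmetry shrank the effect by 0.09 to 0.15, depending on the assumed variances and dropout model. When the mechanism also differed by arm, the shrinkage was 0.15 to 0.31.

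**5. Scale.** 0.05/1.5 = 3% and 0.15/1.5 = 10% of the planning effect. With 0.90 × 120 = 108 completers per group, SE = 3.5 × √(2/108) = 0.476, so 0.05 to 0.15 is about 0.1 to 0.3 of a standard error.

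**The case against.** The best defence is that the plan's sentence is conditional, that compound symmetry with robust standard errors is a recognised choice, and that at the planned retention the effect is small. Much of that stands. If non-informative means missing completely at random, a wrong covariance causes no bias. With 10% loss by the same mechanism in both arms, the bias is 0.01 to 0.02. The documents predict no imbalance in loss. Section 7.4 keeps collecting pain scores to 1 year after treatment failure, which closes one route to score-dependent missingness. Section 9.3 also calls itself a summary and says a separate statistical analysis plan covers missing data. That plan is not in the combined document. None of this changes the covariance that section 9.3.2 states.

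Four stronger readings are tempting, and the documents do not support them:

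- **The model is not identifiable.** A subject random intercept with independent residuals is itself compound symmetry, so the natural reading is one model described twice. If both terms were coded, only their sum would matter (step 2). The wording is redundant but harmless to the fixed effects.
- **Unbiasedness fails whenever the covariance is wrong.** It does not fail with complete data or with missingness completely at random.
- **The difference is pulled toward zero.** The direction depends on the true covariance and the dropout mechanism, which the documents do not give. Step 4 shows both signs.
- **The trial relies on this model alone for missing data.** Without the separate plan this cannot be established.

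**Conclusion.** The point holds as a cheap improvement, not as a flaw that threatens the trial. If non-informative is read as missing at random, the unbiasedness sentence in section 9.3.2 is incomplete: it also needs a correctly specified covariance, which robust standard errors do not supply. Constant variance and correlation across baseline to month 12 are doubtful. At about 10% average loss, the bias is negligible when loss and mechanism are the same in each arm. It is roughly 0.05 to 0.15 VAS points, in either direction, when they differ. Larger values need heavier loss, or subject-specific slopes combined with mechanisms that differ by arm. All these sizes rest on assumed SDs, correlation shapes and dropout models. The stated powers of 91% and 97% are unaffected.

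**What to change.** In section 9.3.2, and in the separate statistical analysis plan if it repeats the text:

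1. State one covariance structure: unstructured over the six time points, with no separate subject random effect and with Kenward-Roger degrees of freedom.
2. Pre-state the order of fallback if the fit does not converge, for example heterogeneous Toeplitz, then heterogeneous AR(1), then compound symmetry with robust standard errors.
3. Restate the unbiasedness sentence as holding under missing at random with a correctly specified covariance, in place of the undefined term non-informative.

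The cost is about one line of SAS code and one edited sentence. The unstructured form has 6 × 7/2 = 21 covariance parameters against 2, with a small risk of non-convergence, which is minor with 480 subjects. Sample size, visits and data collection do not change.
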